5.2.4 Accountability and dispensation

Accurate recording of all IP administered will be made in the appropriate section of the subject's case report form (CRF) and source documents, including patient drug diaries (**Appendix 8**). The subject should bring the drug diary and any empty or partially empty bottles into the clinic for their scheduled visits. The Investigator or designee is accountable for the compliance of all study-specific IP either administered or in their custody during the course of the study.

5.2.5 Disposition of unused investigational study drug

Any unused investigational study drug will be returned to the Pharmacy for proper disposal in accordance with hospital policy of any unused chemotherapeutic agents.

6. TREATMENT PLAN

6.1 Subject enrollment

6.1.1 Assignment of screening number

All consented subjects will be given a unique screening number that will be used to identify the subject for all procedures that occur prior to randomization or treatment allocation. Each subject will be assigned only one screening number. Screening numbers must not be re-used for different subjects. Any subject who is screened multiple times will retain the original screening number assigned at the initial screening visit.

6.1.2 Procedures for randomization

This is not a randomized study. All eligible subjects will be allocated, by non-random assignment, to trial treatment and will receive a unique number. This unique number is termed a randomization number throughout the protocol for operational purposes. The randomization number identifies the subject for all procedures occurring after treatment allocation. Once a randomization number is assigned to a subject, it can never be re-assigned to another subject.

A single subject cannot be assigned more than one unique number. Treatment assignment will be done based on the schema described in **Sections 3.2 and 6.2, Table 2**. All patients will receive the same fixed dose of durvalumab (MEDI4736) and tremelimumab (based on a weight greater than 30 kg) and oral decitabine (ASTX727) will be dose escalated if safe to do so. Enrolled patients will be sequentially assigned to the cohorts. After the enrollment of 6 evaluable patients into the 1st group (eligible patients who at least begin protocol treatment and have an evaluable pre- and on-treatment (8-week) biopsy sample available), the next 6 patients will be enrolled into the 2nd cohort if safe to do so. After the enrollment of 6 evaluable patients into the 2nd cohort, the next 6 patients will be enrolled into the 3rd cohort only if the BED has not been determined, and the group in which the BED has been determined will be expanded to enroll 10 patients. Additional subjects may be enrolled into the cohort(s) to ensure that the required number of evaluable pre- and on-treatment biopsy samples are available to adequately determine the BED. Patients cannot change groups or dose assignments upon the initiation of the study protocol.

6.1.3 Procedures for handling subjects incorrectly enrolled

Subjects who fail to meet the eligibility criteria should not receive study medication. Subjects who are incorrectly enrolled but found to not meet all the eligibility criteria must not be initiated on treatment and must be withdrawn from the study as a screen failure. If a subject, who in error is assigned a randomization number or incorrectly started on treatment, in spite of not

meeting all of the inclusion/exclusion criteria, will be withdrawn from the study and the assigned randomization number will not be re-assigned to another subject and the subject will not be counted toward any treatment cohort.

6.2 Dosage and Administration

This is a phase Ib, open label dose escalation and safety evaluation of durvalumab (MEDI4736) and oral decitabine (ASTX727) combination therapy. This trial opened with the administration of subcutaneous (SC) injection of azacitidine. Treatment i.e. 5 to 10 daily visits for a largevolume SC injection continuing for several months or even years, represents a significant hardship for patients. A possible consequence is non-compliance or earlier discontinuation of a beneficial treatment. Successful development of an oral DNA methyltransferase inhibitor eases the burden of long duration SC therapy, particularly for those patients who are benefiting the most and need continuing treatment for long periods. In our trial with SC injection of azacitidine, we were achieving global tumor hypomethylation with clinical benefit. Furthermore, a tolerable AE profile was being observed. These preliminary results rationalize the continuation of this study but with an oral DNA methyltransferase inihibitor for reasons stated above. Since the oral DNA methyltransferase inhibitor is an investigational drug, we will administer the oral drug with the FDA approved durvalumab. We will continue treatment of azacitidine SC for those patients already enrolled into the study. However, all newly enrolled patients will receive an oral tablet of ASTX727 (35 mg decitabine/100 mg cedazuridine) daily on either Days 1-3, Days 1-4, or Days 1-5, and durvalumab (MEDI4736) 1500 mg via IV infusion x 1 in a 4 week cycle. Oral decatibine (ASTX727) will be administered alone in Cycle 1 and the combination of oral decatibine (ASTX727) and durvalumab therapy will be given in Cycles 2-12 or until confirmed PD, initiation of alternative cancer therapy, unacceptable toxicity, withdrawal of consent, or another discontinuation criterion is met, whichever occurs first. The BED will be assessed on pre-treatment and post-treatment biopsies obtained at week 8. BED is defined as the dose of oral decatibine (ASTX727) that results in at least a 10% decrease in LINE-1 methylation from the baseline biopsy sample to the 8-week on-treatment tumor biopsy sample in at least 50% of patients treated within the same dose level. Accrual will be suspended until assessment of the LINE-1 methylation levels in the first 2 dose cohorts. If the BED has not been determined in the first 2 dose levels and it is safe to do so, then the study will re-open to accrual and a subsequent group of 3 patients will receive the 3rd dose level. If both the first 2 dose levels result in > 10% decrease in LINE-1 methylation, then the dose which induces the greatest fold change in HLA Class I/II APM expression and/or CD8+ T cell infiltration and with the lowest AE profile will be the dose utilized for the dose expansion group. Dose Limiting Toxicity (DLT) will be assessed through 28 days post Cycle 2.

Drug Substance Azacitidine/Decitabine (ASTX727)

Study Code 15-11430

Edition Number 13.0

Date 09202024

Although assessment of the BED is primary, the dose also needs to be safe. Each dose will be assessed for safety according to a stopping rule and a DLT toxicity definition as outlined in the protocol and statistical section. Decisions will then be made about dose escalations of oral decatibine (ASTX727). Subjects will be sequentially assigned to the cohorts. The first 6 enrolled subjects will ingest one tablet daily on Days 1-3 of a 28-day cycle. If two or more of the first six subjects experience a DLT, then the dose will be reduced and an additional six patients will be treated at the reduced dose. If two or more of the six at the reduced dose experience a DLT, then the study will be terminated. If at any time during accrual to a cohort, 2 or more patients in a cohort experience DLT, enrollment to that cohort will be terminated. If less than two of the six patients treated at dose level 1 experience a DLT, a subsequent group of six patients will receive dose level 2.

Patients cannot change groups or dose assignments upon the initiation of the study protocol. Please refer to **Sections 5.1.2, 5.1.3, and 5.2.4**. for the administration and monitoring of administration of durvalumab (MEDI4736) and tremelimumab. Please refer to **Section 5.3** for the administration and monitoring of administration of oral decitabine (ASTX727).

Table 5a: Cohort size and dose escalation for oral decitabine (ASTX727)

Cohort (# of pts)	Oral decitabine (ASTX727) (28 day cycle)	Grade 3 or higher	2-fold DNMT1 inhibition in ≥50% of patients
BD-1 (6)	ASTX 727 one tablet daily on Days 1-2	MTD ¹	BED ²
B1 (6)	ASTX 727 one tablet daily on Days 1-3	MTD ¹	BED ²
B2 (6)	ASTX 727 one tablet daily on Days 1-4	MTD ¹	BED ²
B3 (6)	ASTX 727 one tablet daily on Days 1-5	MTD ¹	BED ²

 $^{^{1}}$ MTD (maximally tolerated dose) will be defined as that dose of azacitidine that results in \leq 2 of 6 patients experiencing a DLT

Table 5b: Cohort size and dose escalation for azacitidine

²BED (biologically effective dose) will be defined as that dose of oral decitabine (ASTX727) that results in at least a 10% decrease in LINE-1 methylation in pre- and on-treatment biopsy samples in >50% of treated subjects

Drug Substance Azacitidine/Decitabine (ASTX727)

Study Code 15-11430

Edition Number 13.0

Date 09202024

Cohort (# of pts)	Azacitidine (28-day cycle)	Grade 3 or higher	2-fold DNMT1 inhibition in ≥50% of patients
D-1 (6)	20 mg/m2 on Days 1-5	MTD ²	BED ³
1 (6)	40 mg/m2 on Days 1-5	MTD ²	BED ³
2 (6)	40 mg/m2 on Days 1-5 and 8-12	MTD ²	BED ³
3 (6)	75 mg/m2 on Days 1-5	MTD ²	BED ³

The overall safety of the combination therapy will be evaluated by following patients up to 28 days for DLTs after the first dose of oral decitabine (ASTX727) and durvalumab (MEDI4736) combination therapy (end of cycle 2 (which is the first cycle of the combination)).

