2. STUDY OBJECTIVE

2.1.1 Primary objective(s)

To determine the Biologically Effective Dose (BED) of oral decitabine (ASTX727) in combination with durvalumab (MEDI4736) therapy.

2.1.2 Secondary Objective:

To assess the safety of oral decitabine (ASTX727) in combination with durvalumab (MEDI4736) therapy.

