Although assessment of the BED is primary, the dose also needs to be safe. Each dose will be assessed for safety according to a stopping rule and a DLT toxicity definition as outlined in the protocol and statistical section. Subjects will be sequentially assigned to the cohorts. The first 6 enrolled subjects will receive one tablet daily on Days 1-3 of a 28-day cycle. If two or more of the first six subjects experience a DLT, then the dose will be reduced and an additional six patients will be treated at the reduced dose. If two or more of the six at the reduced dose experience a DLT, then the study will be terminated. If at any time during accrual to a cohort, 2 or more patients in a cohort experience DLT, enrollment to that cohort will be terminated. If less than two of the six patients treated at dose level 1 experience a DLT, a subsequent group of six patients will receive dose level 2.

Subjects cannot change groups or dose assignments upon the initiation of the study protocol.

Tumor assessments will be performed using CT or MRI. Efficacy and survival for all patients will be assessed by objective tumor assessments every 8 weeks (q8w) +/- 7 days for the first 48 weeks (relative to the date of the first infusion) then q12w in patients who have disease control after 12 months until confirmed objective disease progression as defined by Response Evaluation Criteria in Solid Tumors (RECIST) version 1.1. Categorization of objective tumor response assessment will be based on RECIST 1.1: complete response (CR), partial response (PR), stable disease (SD), and progressive disease (PD). Objective tumor response (CR or PR) will be confirmed at the next scheduled visit and not less than 4 weeks after the visit when the response was first observed. All scans showing PD should be confirmed at the next scheduled

Drug Substance Azacitidine/Decitabine (ASTX727)

Study Code 15-11430

Edition Number 13.0

Date 09202024

visit and no earlier than 4 weeks after the initial assessment of PD in the absence of clinically significant deterioration. Treatment with IP should continue between the initial assessment of progression and its confirmation. If progression is not confirmed, then the patient should continue receiving study treatment and participate in study assessments.

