6.3 Dose Escalation Decision Rules

Dose escalation monitoring

In order to ensure that patients are receiving the assigned dose of drug, oral decitabine (ASTX727), several measures will be employed.

Printed orders will be available.

The principal investigator, research nurse, and data manager will review the available toxicity data prior to continuing to escalate the dose and enrolling patients into the new cohort.

Prior to the start of each new dose level (i.e. accrual of a new cohort), a dated letter will be sent to the pharmacy which describes the change in dose.

Stopping rules

Dose escalations will continue until one of the following stopping rules has been satisfied:

- 1. The BED has been determined.
- 2.If at any time during accrual to a cohort, 2 or more patients in a dose cohort experience DLT, enrollment to that dose cohort will be terminated and dose escalation will stop.
- 3. Two of six patients treated at a reduced dose of oral decitabine (ASTX727) on Days 1-2 of a 28 day cycle experience a DLT

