Although assessment of the BED is primary, the dose also needs to be safe. Each dose will also be assessed for safety. Six patients will be entered into dose level 1. Adverse events (i.e. dose limiting toxicity (DLT) assessment as defined in section 6.4) will be assessed through 28 days post cycle 2. If two or more of the first six subjects experience a DLT, then the dose will be reduced and an additional six patients will be treated at the reduced dose. If two or more of the six at the reduced dose experience a DLT, then the study will be terminated. If at any time during accrual to a dose cohort, 2 or more patients in a dose cohort experience DLT, enrollment to that dose cohort will be terminated. If less than two of the six patients treated at dose level 1 experience a DLT, a subsequent group of six patients will receive dose level 2.

Drug Substance Azacitidine/Decitabine (ASTX727)

Study Code 15-11430

Edition Number 13.0

Date 09202024

Accrual will be suspended until review of the BED rate in tissue from baseline and 8 weeks post baseline has been completed from patients entered into the first 2 dose levels. If the BED has not been determined in the first 2 dose levels and it is safe to do so, then the study will re-open to accrual and a subsequent group of 6 patients will receive the 3rd dose level. Once the BED is determined, dose escalation will stop and the BED will be used in the expansion cohort.

Approximately 28 evaluable patients (eligible patients who at least begin protocol treatment and have an evaluable pre- and on-treatment (8-week) biopsy sample available) are estimated to be accrued during the BED assessment phase with the oral decitabine. This is based on studying 6 evaluable patients per dose level with a total of 3 dose levelsand an additional 10 evaluable patients entered at the BED ('expansion cohort' accrued to ensure that the BED rate is acceptable). The further assessment of the BED will be based on studying these 10 additional patients. Additional subjects may be enrolled into the cohort(s) to ensure that the required number of evaluable pre- and on-treatment biopsy samples are available to adequately determine the BED. See end of this statistical section for overall sample size.

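### The MTD footnote in Table 5a accepts 2 DLTs in 6, which every stopping rule treats as unacceptable, and names azacitidine instead of oral decitabine

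*Combined protocol and SAP*

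**What the plan says.** Footnote 1 of Table 5a (Section 6.2) is attached to cohorts BD-1, B1, B2 and B3, all of them ASTX727 schedules. It says "MTD (maximally tolerated dose) will be defined as that dose of azacitidine that results in", then a less-than-or-equal sign, then "2 of 6 patients experiencing a DLT". Footnote 2 of the same table, on the BED, correctly names oral decitabine. Section 3.2 only spells out the abbreviation MTD, so footnote 1 is the one numeric definition of the MTD in the text.

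The operative safety rules are:

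- Dose level 1 (Section 6.2, repeated in 3.1 and 11): "If two or more of the first six subjects experience a DLT, then the dose will be reduced".
- Reduced dose (Section 3.1, repeated in 6.2 and 11): "If two or more of the six at the reduced dose experience a DLT, then the study will be terminated".
- Opening level 2 (Section 11, repeated in 3.1 and 6.2): allowed "If less than two of the six patients treated at dose level 1 experience a DLT".
- Any cohort (Section 6.3, stopping rule 2): "2 or more patients in a dose cohort experience DLT, enrollment to that dose cohort will be terminated and dose escalation will stop".
- Stopping rule 3 (Section 6.3): escalation ends if a DLT occurs in "Two of six patients treated at a reduced dose of oral decitabine (ASTX727) on Days 1-2".

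The primary objective (Section 2.1.1) is "To determine the Biologically Effective Dose (BED) of oral decitabine (ASTX727" in combination with durvalumab. Finding an MTD is not listed as an objective.

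**The concern.** The plan has already fixed its tolerability limit, and it is the same in four sections: 0 or 1 DLT in six is acceptable, 2 or more is not. Footnote 1 moves that limit by one patient. This is therefore an internal contradiction and not a debate about which threshold is best.

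What is at stake is the label on a dose. A dose closed for toxicity could be reported as the MTD, that is, as tolerated. The opening for this is widest at levels 2 and 3. There, stopping rule 2 ends enrollment and escalation, but the plan does not say which dose goes forward, and the only numeric definition of a tolerated dose would admit the one just stopped. The wrong drug name adds a second defect: read literally, the oral table contains no MTD definition for the oral drug.

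**Working it through.** **Side by side.** For each possible DLT count in a completed six-patient cohort:

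| DLTs in 6 | Stopping rules (3.1, 6.2, 6.3, 11) | Footnote 1 |
|---|---|---|
| 0 or 1 | acceptable; level 1 may escalate | qualifies as MTD |
| 2 | reduce, close the cohort, or end the study | qualifies as MTD |
| 3 or more | reduce, close the cohort, or end the study | does not qualify |

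The two disagree in one row only, at exactly 2 of 6. The clearest instance is BD-1 (Days 1-2). Stopping rule 3 and Section 3.1 make two of six there a stop, while footnote 1, attached to the BD-1 row, would call the same result the MTD.

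**How often that row occurs.** The plan states no operating characteristics for its DLT rule; the probabilities in Section 11 concern the BED only. It also gives no true DLT rate, so I assume *p* = 20%, 30%, 33% (1/3) and 40%.

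*Upper end.* No DLT is known until all six are enrolled. P(X = 2) = 15 p²(1−p)⁴:

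- 20%: 15 × 0.04 × 0.4096 = 0.246
- 30%: 15 × 0.09 × 0.2401 = 0.324
- 33%: 15 × 0.1111 × 0.1975 = 0.329
- 40%: 15 × 0.16 × 0.1296 = 0.311

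*Lower end.* Every DLT is known before the next patient enters, so the cohort fills and ends at 2 only if the first five contain one DLT and the sixth patient has the second. The probability is 5p(1−p)⁴ × p = 5p²(1−p)⁴, one third of the upper end: 0.082, 0.108, 0.110, 0.104.

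*At the planned pace.* Section 11 expects 2 patients per month, or one every 15.2 days. Section 6.4 runs the DLT window to the end of Cycle 2, which is 2 × 28 = 56 days. With DLT times assumed uniform over 0 to 56 days and enrollment closed once 2 DLTs have occurred, simulation of 400,000 cohorts gives P(six enrolled and exactly 2 DLTs) = 0.162, 0.215, 0.217, 0.206.

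**What the label would admit.** Taking full cohorts of six, P(at most 1 DLT) = (1−p)⁶ + 6p(1−p)⁵, and P(at most 2) adds the upper-end term above:

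| True DLT rate | At most 1 of 6 (stopping rules) | At most 2 of 6 (footnote 1) |
|---|---|---|
| 20% | 0.655 | 0.901 |
| 30% | 0.420 | 0.744 |
| 33% | 0.351 | 0.680 |
| 40% | 0.233 | 0.544 |

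At a true rate of 40% the footnote would label the dose tolerated more than twice as often as the stopping rules would accept it (0.544 / 0.233 = 2.3).

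**The case against.** Four points can be made for leaving this as a small editorial matter.

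*The threshold conflict hangs on one character.* The supplied text was extracted from a PDF, and signs near this footnote are not uniform: footnote 2 has a strict sign for the 50% criterion where the column header and Section 6.3.1 mean at least 50%. If the source of footnote 1 showed a strict sign, it would match the stopping rules. The sign should be checked against the source. But the text as supplied has an explicit less-than-or-equal sign, nothing shows that it is wrong, and the drug name would need correcting either way.

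*Nothing depends on the MTD.* This stands. Escalation, reduction and termination run on the explicit 2-or-more rules, and the expansion dose is chosen on the BED, a marker panel and the adverse event profile. That is why the harm is confined to labelling.

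*The planned-pace figures depend on assumptions.* This also stands. Sections 3.1, 6.2 and 11 speak of DLT assessment through 28 days after Cycle 2, which could be read as about 84 days. Durvalumab starts only in Cycle 2, so DLTs may cluster late. Re-running with a uniform 84-day window, or with DLTs confined to days 28 to 56, gives about 20% to 27% over the same DLT rates. These values are higher than those for the uniform 56-day window and stay within the stated bounds. Section 6.4 and the closing paragraph of Section 6.2 both put the end of the window at the end of Cycle 2, which supports 56 days.

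*The drug name is an obvious carry-over from the azacitidine design.* Probably so, and few readers would be misled by it alone. It is still an error in the operative dose table.

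**Conclusion.** The concern holds. Footnote 1 contradicts a threshold that the plan states consistently elsewhere, and it names a drug that its table does not cover. The contradiction bites only at exactly 2 of 6 DLTs. For assumed true DLT rates of 20% to 40%, that outcome has a probability of 8% to 33% across the extremes of DLT reporting speed, and about 16% to 22% at the planned accrual with a 56-day window and uniform DLT times. These are frequencies of conflicting labels, not of patients harmed: no cohort opens, closes or changes dose because of the footnote. It should be fixed because, as written, it lets a dose stopped for toxicity be reported as tolerated. The threshold part assumes that the inequality sign in the supplied text is faithful to the source; the drug-name part does not.

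**What to change.** Replace footnote 1 of Table 5a with: *MTD: the highest dose of oral decitabine (ASTX727) at which fewer than 2 (at most 1) of 6 patients experience a DLT.* This corrects the drug, aligns the limit with Sections 3.1, 6.2, 6.3 and 11, and adds the word highest, without which several dose levels could meet the definition at once. The threshold itself does not need to be reconsidered.

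The footnote edit does not settle which dose is carried forward when 2 DLTs occur at level 2 or 3. One optional sentence in Section 6.3 naming that dose would do so.

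The cost is one footnote, plus that sentence if wanted, in the next amendment. It needs no extra patients and no change to the operative rules.

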6.3 Dose Escalation Decision Rules

Dose escalation monitoring

In order to ensure that patients are receiving the assigned dose of drug, oral decitabine (ASTX727), several measures will be employed.

Printed orders will be available.

The principal investigator, research nurse, and data manager will review the available toxicity data prior to continuing to escalate the dose and enrolling patients into the new cohort.

Prior to the start of each new dose level (i.e. accrual of a new cohort), a dated letter will be sent to the pharmacy which describes the change in dose.

Stopping rules

Dose escalations will continue until one of the following stopping rules has been satisfied:

- 1. The BED has been determined.
- 2.If at any time during accrual to a cohort, 2 or more patients in a dose cohort experience DLT, enrollment to that dose cohort will be terminated and dose escalation will stop.
- 3. Two of six patients treated at a reduced dose of oral decitabine (ASTX727) on Days 1-2 of a 28 day cycle experience a DLT

